3. STUDY DESIGN AND METHODS

This is a pilot study of Phase II clinical trial design to evaluate the safety and efficacy of Campath in subjects with T-LGL leukemia. Alemtuzumab (Campath®) will be administered off label at 10 mg per day by intravenous infusion for 10 days total and then subjects will be monitored for up to 5 years to assess efficacy and safety endpoints. Subjects who do not respond to initial cycle or relapse may receive a second cycle of drug after the 3 month time point.

4. ELIGIBILITY ASSESSMENT

4.1 Inclusion Criteria

4.1.1 Clinical history supportive of the diagnosis of T-LGL leukemia (i.e. a history of cytopenias with

peripheral blood morphologic evidence of LGLs)

4.1.2 Immunophenotypic studies of peripheral blood showing an increased population of T-LGLs (suggested by staining with CD3+, CD8+ and CD16+ or CD57+) or gamma-delta T cells.

4.1.3 Restricted or clonal rearrangement of the T-cell receptor by PCR **AND one or more of the following**

Severe neutropenia (< 500 neutrophils/ μ L);

OR

Severe thrombocytopenia (< 20,000 platelets/ μ L), or moderate thrombocytopenia (< 50,000 platelets/ μ L) with active bleeding;

OR

Symptomatic anemia with a hemoglobin < 9 g/dL or red blood cell transfusion requirement of > 2 units/month for two months prior to initiation of Campath

4.1.4 Age 18-85 (both inclusive)

4.2 Exclusion Criteria

4.2.1 A reactive LGL lymphocytosis to a viral infection

4.2.2 Serologic evidence of HIV infection

4.2.3 Infection not adequately responding to appropriate therapy

4.2.4 Previous immunosuppressive therapy with alemtuzumab

4.2.5 History of carcinoma that is not considered cured (excluding non-melanoma skin carcinoma)

4.2.6 Moribund status or concurrent hepatic, renal, cardiac, neurologic, pulmonary, infectious, or metabolic disease of such severity that it would preclude the subject's ability to tolerate protocol therapy or that death within 7-10 days is likely.

4.2.7 Current pregnancy, or unwilling to take oral contraceptives or refrain from pregnancy if of childbearing potential

4.2.8 Not able to understand the investigational nature of the study or give informed consent

5 TREATMENT PLAN

5.1. Alemtuzumab (Campath®) Administration

All subjects will initially receive a test dose of 1 mg in 100 ml NS given intravenously over 1 hour.

If tolerated, alemtuzumab (Campath®) will be administered at 10 mg/dose IV for 10 days as an infusion over 2 hours.

Subjects will be admitted to the Clinical Center hospital for study drug initiation. If the study drug infusion is tolerated well (toxicity \leq grade 2) the subject may be discharged and receive the remainder of the treatment course as an outpatient.

5.2 Re-treatment (per PI discretion)

Subjects who do not respond to initial cycle or relapse following initial treatment may be retreated at the discretion of principal investigator with an additional cycle of Campath 10 mg/dose IV for 10 days anytime after the 3 month (primary assessment) time point.

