6.1 Pre-study Evaluation

Baseline status will be evaluated as follows:

- Medical History and physical examination
- Baseline laboratory studies
 - Complete blood count with differential
 - Reticulocyte count
 - DAT (direct antiglobulin test)
 - Chem 20 panel
 - Pregnancy test (urine or blood HCG in women of child bearing potential)
 - Folate level
 - B12 level

Coagulation screen (PT, PTT)
Iron panel (ferritin, transferrin, % saturation)

- Thyroid function tests
- Viral serologies for hepatitis A, B, C, HIV, HSV, HTLV I/II
- Antinuclear antibody (ANA)
- Rheumatoid factor (RF)
- Serum protein electrophoresis (SPEP)
- Quantitative serum immunoglobulins
- Urine protein electrophoresis (UPEP)
- EBV and CMV PCR in the blood prior to treatment
- Bone marrow aspirate and biopsy with cytogenetic
- Peripheral blood flow cytometry
- T-cell receptor (TCR) gene rearrangement studies
- HLA typing (if not already available)
- Chest X-ray
- Serum troponin before first dose of alemtuzumab (Campath®),
- ECHO, 24 hour Holter monitor before first dose of alemtuzumab (Campath®)
- EKG on the day of admission
- A research apheresis collection (see section 7.0, Lab research studies)

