6.2 On study drug monitoring: (cycle 1 and if applicable cycle 2)

On treatment monitoring will consist of:

- CBC with differential (daily)
- Chem 20 panel (every other day)
- Reticulocyte count (weekly +/- 3 days)
- Vital signs (daily)
- ECHO and 24 hour Holter monitor after last dose alemtuzumab (Campath®)
- Serum troponin at day 5 and after the last dose of alemtuzumab (Campath®)
- EBV and CMV PCR in the blood (weekly +/- 3 days)
- Chest x-ray, CT scans or appropriate imaging studies (only as medically indicated)

6.3 Post treatment monitoring discharge home through 3 months: After completing treatment, subjects will be followed by their home physician or at the Clinical Center and have blood work done as detailed below. Progress notes and laboratory results from home physicians will be faxed to [name], R.N., Research Nurse. Subjects must be evaluated at the Clinical Center at the 3 month (± 7 days) time point

- Interim Assessment
- Complete blood counts with differential (weekly +/- 3 days)
- DAT (NIH) or Coombs test (monthly +/- 2 weeks)
- Chem 20 panel (weekly +/- 3 days) (Home MDs: electrolytes, transaminases, urea nitrogen (BUN), serum creatinine, total bilirubin)
- EBV and CMV PCR in the blood (weekly +/- 3 days) for the first month, then every other week +/- 3 days) in the second month, and then monthly (+/- 2 weeks)
- Reticulocyte count (at 3 months only +/- 2 wks, home MDs only if available)
- ECHO (at 3 months only +/- 2 wks)
- Serum troponin (at 3 months only +/- 2 wks)

- Thyroid function tests (at 3 months only +/- 2 wks)
- Peripheral blood flow cytometry (at 3 months only +/- 2 wks)

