8.6 Off study criteria

Per Subject choice: Subjects may be removed from study at their request. The risks of withdrawing will be discussed, as will alternative treatment options.

Per principal investigator decision: Alemtuzumab (Campath®) administration will be discontinued; the subject will be followed until the event has resolved if the subject develops:

- Intolerance of alemtuzumab (Campath®) infusion as manifested by hypotension, fever, chills and/or rash that is refractory to supportive measures; OR any subject who develops CTCAE grade 4 hepatic injury or DIC subsequent to infusions of alemtuzumab.
- Life threatening acute hypersensitivity reactions
- Pregnancy or unwillingness to refrain from pregnancy
- Initiation of additional immunosuppressive therapy (except steroids or CsA)
- Failure to respond to Campath therapy
- Subject non-compliance
- Lost to follow-up

- Study completion

Those subjects who choose to withdraw or are removed from the study per PI decision will be asked to continue to have labs monitored through the 6 month off drug time point so that we can continue to monitor for post Campath related safety issues. Once off study subjects will be referred back to his or her referring physician or consented to the Hematology Branch evaluation and treatment protocol (94-H-0010) for consideration for standard therapy or evaluation for eligibility for another branch protocol, depending on what is considered to be in the best interest of the subject.

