Cardiac toxicities: The following were reported in at least one patient treated on studies where alemtuzumab was used as a single agent: cardiac failure, cyanosis, atrial fibrillation, cardiac arrest, ventricular arrhythmia, ventricular tachycardia, angina pectoris, coronary artery disorder, myocardial infarction, and pericarditis. Some of these cardiac abnormalities may be irreversible. For this reason, we will monitor subjects with an echocardiogram and a 24 hour Holter monitor before treatment begins and after the last dose of alemtuzumab (Campath®). The ECHO will also be repeated at the 3 month follow up visit. We will closely monitor subjects for cardiac symptomology and ask them to immediately report any cardiac symptoms (palpitations, irregular pulse, difficulty in breathing, dizziness, swelling in the ankles, chest discomfort or pain).

Hematologic toxicities: Myelosuppression involves all 3 cell lineages. Serious and in rare instances fatal pancytopenia/marrow hypoplasia, autoimmune idiopathic thrombocytopenia, and autoimmune hemolytic anemia have occurred in patients receiving alemtuzumab (Campath®).

Other side effects (> 5% in CLL studies) include headache, anorexia, asthenia, skeletal pain, myalgias, peripheral edema, dyesthesias, dizziness, tremor, stomatitis, mucositis, dyspnea, cough, pneumonitis, rhinitis, abdominal pain, back pain, dyspepsia, constipation, insomnia, depression, somnolence, diarrhea, and EBV related lymphoproliferative disease.

Pregnancy and breast feeding: Animal reproductive studies have not been conducted. It is not known whether alemtuzumab can affect reproductive capacity or cause fetal harm. Human IgG is known to pass the placental barrier and thus may potentially cause fetal B-cell depletion; therefore alemtuzumab should only be given to pregnant women only if clearly needed. It is not known whether alemtuzumab is excreted in human milk. Because human IgG is excreted in human milk and the potential for absorption and immunosuppression in the infant is unknown, women should be advised to discontinue nursing for at least 3 months following last dose of alemtuzumab (Campath®).

10.3.2 Related to bone marrow aspirate and biopsy: No major risks are involved with bone marrow aspirate and biopsy. However, a small risk of infections, pain, bleeding, and hematoma formation at the site of the aspiration exists with the procedure.

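### A second alemtuzumab cycle can start any time after month 3 without a repeat pregnancy test; the only scheduled HCG is at baseline

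*Combined protocol and SAP*

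**What the plan says.** Section 5.2 permits retreatment, at the principal investigator's discretion, of subjects who do not respond or who relapse, "with an additional cycle of Campath 10 mg/dose IV for 10 days anytime after the 3 month (primary assessment) time point". It sets no latest date, asks for no pre-dose tests and does not call for eligibility to be checked again.

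The baseline list in 6.1 includes "Pregnancy test (urine or blood HCG in women of child bearing potential". Section 6.2 is headed "On study drug monitoring: (cycle 1 and if applicable cycle 2", so it is the list that governs the second course.

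Three other provisions bear on pregnancy:

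- Section 4.2.7 excludes at entry: "Current pregnancy, or unwilling to take oral contraceptives or refrain from pregnancy if of childbearing potential".
- Section 8.6 lists among the reasons for discontinuing alemtuzumab: "Pregnancy or unwillingness to refrain from pregnancy".
- Section 10.3.1 states the hazard: "Human IgG is known to pass the placental barrier and thus may potentially cause fetal B-cell depletion". It adds that "alemtuzumab should only be given to pregnant women only if clearly needed", and says that the drug's potential for fetal harm is unknown.

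**The concern.** The plan tests for pregnancy before the first course but not before the second, which uses the same drug at the same daily dose for the same number of days. No reason for the difference is given. By the time cycle 2 starts, the baseline result says nothing about current status.

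What is at stake is patient and fetal safety. Section 10.3.1 makes use in pregnancy depend on a judgement of need, and 8.6 makes pregnancy a reason to stop drug. Both work only if the pregnancy is known before the infusion. The main route to harm is a contraceptive failure or lapse after enrolment that nobody has yet noticed.

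**Working it through.** No plan figure has to be reproduced here. The check is a reading of every place where a pre-cycle-2 pregnancy test could be required, followed by a bound on how many subjects it could concern.

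**Step 1: where an HCG is scheduled**

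| Section | Covers | HCG listed |
|---|---|---|
| 5.2 | Retreatment | No |
| 6.1 | Baseline | Yes, once |
| 6.2 | On drug, cycles 1 and 2 | No |
| 6.3 | Discharge to 3 months | No |
| 6.4 | 3 to 6 months | No |
| 6.5 | After 6 months | No |

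The eight items in 6.2 are blood count, chemistry panel, reticulocytes, vital signs, ECHO with Holter, troponin, EBV/CMV PCR, and imaging when indicated. HCG accounts for 0 of 8. The protocol does carry some procedures forward to cycle 2: the 6.2 list itself, and the research blood samples in 7.1. The pregnancy test is not among them.

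**Step 2: age of the baseline HCG at cycle 2**

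Retreatment is allowed only after the 3-month time point, so the result is more than 3 months old. Section 5.2 sets no upper limit, relapse is a permitted trigger, and section 3 provides for up to 5 years of monitoring. The result could therefore be years old.

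**Step 3: whether the other controls fill the gap**

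- 4.2.7 is an entry criterion, and 5.2 does not say it is applied again before cycle 2.
- 8.6 continues to apply during the study, so it bars retreating a woman known to be pregnant. It cannot act on a pregnancy that no test has detected.

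**Step 4: how many subjects**

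- Maximum enrolment (8.3): 19 + 20 = 39.
- Eligible ages (4.1.4): "Age 18-85 (both inclusive", so women of childbearing potential can enrol, and 6.1 provides for them.
- Section 2.1 says the disease is most common after age 50, so few are expected.
- The share of women of childbearing potential is not in the documents. Assumed range 0% to 10%: 39 × 0 = 0, and 39 × 0.10 = 3.9, or about 4.
- Only those retreated are exposed to the gap, so the relevant number is lower. Retreatment is nevertheless a realistic path: section 2.5 reports that some patients do not respond and that some responders show signs of relapse.

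**The case against.** The strongest case on the other side is that the exposure is remote and partly controlled. A subject would have to be of childbearing potential in a disease mostly of older people, fail or relapse, be chosen for retreatment, and be unknowingly pregnant despite the entry condition on contraception. Retreatment is discretionary, and visits to the Clinical Center at 3 and 6 months are mandatory, so a sensible investigator would probably test. This is fair on frequency. It does not supply a test: no HCG is listed at those visits, and the protocol did not leave the matter to judgement at cycle 1.

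A second point is that 6.2 is an on-treatment list and has no HCG for cycle 1 either, because pre-dose checks sit in 6.1. The zero-of-eight count therefore shows only that the test is absent from that list. This stands, and it makes 5.2 the natural home for the requirement. The gap itself is unchanged, since nothing says that the 6.1 work-up is repeated.

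Third, the pre-dose EKG, troponin and ECHO/Holter in 6.1 are not restated for cycle 2 either, so the omission may be general brevity rather than a specific oversight. That may explain how it arose, but brevity does not protect the patient.

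Fourth, the fetal-risk wording is precautionary and documents no established harm. That is correct. It is still the protocol's own reason for wanting to know pregnancy status before a dose.

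**Conclusion.** The concern holds. One test is missing at one time point, before the first dose of cycle 2, and the existing safeguards do not detect an unrecognised pregnancy. The number of women affected is probably small and may be zero. The figure of 0 to about 4 of 39 rests on an assumed 0% to 10% share of women of childbearing potential and is taken before retreatment is counted.

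The change should be made because the possible harm is serious and the remedy is one routine test. It is a safety matter only: the primary endpoint, sample size, error rates and stopping rule are untouched.

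One limit applies. The title and consent pages and a short part of section 9.2 were not available, so wording there cannot be excluded. The treatment and evaluation sections, where such a requirement belongs, were read and do not contain it.

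**What to change.** Add one sentence to 5.2, for example: *In women of childbearing potential, a negative urine or blood HCG is required before the first dose of cycle 2.* Add a matching item to 6.2, marked as a pre-dose test for cycle 2, so that the list used at the bedside agrees with 5.2. Dose, timing and investigator discretion for retreatment stay as they are.

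The cost is one sentence of amendment text, the matching list item, and one urine or blood test for each retreated woman of childbearing potential. The downside is that a retreatment may occasionally be delayed or withheld.

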5.3 Pre-medications and management of infusion reactions

Subjects will receive pre-medication with oral diphenhydramine 50 mg and acetaminophen 650 mg 30 minutes prior to infusion.

Infusions reactions will be treated symptomatically (e.g., anti-emetics, IV fluid hydration, acetaminophen, antihistamines, inhaled bronchodilators).

In case of moderate or severe reactions hydrocortisone will be given and the infusion will be discontinued and restarted at a slower rate once the symptoms have subsided.

If a subject has a persistent severe infusion reaction to alemtuzumab (Campath®) that does not respond to measures to ameliorate the signs/symptoms associated to the infusion, the infusion will be discontinued and the subject will be followed for 6 months then taken off study (see section 9.6).

5.4 Permitted supportive care

- Transfusional supportive care (e.g., blood and platelets) as clinically indicated.
- Growth factors if deemed necessary by the investigator or treating physician

5.5 Infection Prophylaxis and Monitoring

- **Pneumocystis prophylaxis:** Aerosolized pentamidine will be used as prophylaxis against *Pneumocystis jiroveci*, 300 mg every 4 weeks by inhalation beginning the first month of therapy and to continue for at least 6 months. If at 6 months CD4+ cells are $< 200 /\mu\text{L}$, *Pneumocystis jiroveci* prophylaxis will be continued until CD4+ cells $> 200 /\mu\text{L}$. Trimethoprim/sulfamethoxazole, Dapsone or other prophylactic regimen against *Pneumocystis carinii* may be substituted at the discretion of the PI.
- **Antiviral prophylaxis:** Valacyclovir 500 mg once daily will be given for at least 2 months to subjects regardless of HSV serology status. If at 2 months CD4+ cells are $< 200 /\mu\text{L}$, antiviral prophylaxis will be continued until CD4+ cells $\geq 200 /\mu\text{L}$
- **Antibacterial prophylaxis:** Ciprofloxacin 500 mg BID until ANC $> 200 /\mu\text{L}$ (in subjects with ANC $< 200 /\mu\text{L}$ only). This drug may be continued at the discretion of the PI.

- **EBV and CMV Monitoring:** Subjects will be monitored for EBV and CMV PCR in the blood prior to treatment, then weekly for the first month, every other week in the second month, monthly for another 6 months and at 12 months. In case of a positive PCR for CMV, treatment will be instituted when clinical symptoms are attributed to CMV. EBV positivity by PCR will also be placed in context of clinical signs and symptoms.

5.6 Fever Management of Neutropenic Patients

Subjects with a single temperature of 38.5 °C or two readings of 38.0 °C or greater will be evaluated for infection including cultures of blood and urine and any other suspicious sites prior to beginning empiric therapy. Antibiotics will be initiated following current infectious disease guidelines.

5.7 Instructions to patients

Subjects, who have recently received alemtuzumab (Campath®), should not be immunized with live viral vaccines due to the immunosuppression. In addition, other persons living in the household should not take oral polio vaccine since there is a chance they could pass the polio virus on to the subject. Subjects will be instructed to avoid persons who have taken oral polio vaccine within the last several months, not to get close to them, or stay in the same room with them for very long. If they cannot take these precautions, they will be instructed to consider wearing a protective face mask that covers the nose and mouth.

Subjects who develop hypersensitivity to alemtuzumab (Campath®) will be advised they may have an allergic or hypersensitivity reaction to other monoclonal antibodies.

6 CLINICAL EVALUATION

Bone marrow aspirate will be read by a pathologist and used for diagnostic purposes. Samples will be ordered and tracked through the CRIS Screens. Should a CRIS screen not be available, the NIH form 2803-1 will be completed and will accompany the specimen and be filed in the medical record.

Screening evaluations may be performed or obtained from testing performed under 97-H-0041 (Hematology Branch Screening Protocol) or other applicable IRB protocols.

6.1 Pre-study Evaluation

Baseline status will be evaluated as follows:

- Medical History and physical examination
- Baseline laboratory studies
 - Complete blood count with differential
 - Reticulocyte count
 - DAT (direct antiglobulin test)
 - Chem 20 panel
 - Pregnancy test (urine or blood HCG in women of child bearing potential)
 - Folate level
 - B12 level

Coagulation screen (PT, PTT)
Iron panel (ferritin, transferrin, % saturation)

- Thyroid function tests
- Viral serologies for hepatitis A, B, C, HIV, HSV, HTLV I/II
- Antinuclear antibody (ANA)
- Rheumatoid factor (RF)
- Serum protein electrophoresis (SPEP)
- Quantitative serum immunoglobulins
- Urine protein electrophoresis (UPEP)
- EBV and CMV PCR in the blood prior to treatment
- Bone marrow aspirate and biopsy with cytogenetic
- Peripheral blood flow cytometry
- T-cell receptor (TCR) gene rearrangement studies
- HLA typing (if not already available)
- Chest X-ray
- Serum troponin before first dose of alemtuzumab (Campath®),
- ECHO, 24 hour Holter monitor before first dose of alemtuzumab (Campath®)
- EKG on the day of admission
- A research apheresis collection (see section 7.0, Lab research studies)

6.2 On study drug monitoring: (cycle 1 and if applicable cycle 2)

On treatment monitoring will consist of:

- CBC with differential (daily)
- Chem 20 panel (every other day)
- Reticulocyte count (weekly +/- 3 days)
- Vital signs (daily)
- ECHO and 24 hour Holter monitor after last dose alemtuzumab (Campath®)
- Serum troponin at day 5 and after the last dose of alemtuzumab (Campath®)
- EBV and CMV PCR in the blood (weekly +/- 3 days)
- Chest x-ray, CT scans or appropriate imaging studies (only as medically indicated)

6.3 Post treatment monitoring discharge home through 3 months: After completing treatment, subjects will be followed by their home physician or at the Clinical Center and have blood work done as detailed below. Progress notes and laboratory results from home physicians will be faxed to [name], R.N., Research Nurse. Subjects must be evaluated at the Clinical Center at the 3 month (± 7 days) time point

- Interim Assessment
- Complete blood counts with differential (weekly +/- 3 days)
- DAT (NIH) or Coombs test (monthly +/- 2 weeks)
- Chem 20 panel (weekly +/- 3 days) (Home MDs: electrolytes, transaminases, urea nitrogen (BUN), serum creatinine, total bilirubin)
- EBV and CMV PCR in the blood (weekly +/- 3 days) for the first month, then every other week +/- 3 days) in the second month, and then monthly (+/- 2 weeks)
- Reticulocyte count (at 3 months only +/- 2 wks, home MDs only if available)
- ECHO (at 3 months only +/- 2 wks)
- Serum troponin (at 3 months only +/- 2 wks)

- Thyroid function tests (at 3 months only +/- 2 wks)
- Peripheral blood flow cytometry (at 3 months only +/- 2 wks)

6.4 Post treatment monitoring 3 months to 6 months

After the 3 month visit, subjects will be followed by their home physician or at the Clinical Center and have blood work done as detailed below. Progress notes and laboratory results from home physicians will be faxed to [name], R.N., Research Nurse. Subjects must be evaluated at the Clinical Center at the 6 month (+/-2 wks) time point

- Complete blood counts with differential (every other week +/- 3 days)
- DAT (NIH) or Coombs test
- Chem 20 panel (every other week +/- 3 days) (Home MDs: electrolytes, transaminases, urea nitrogen (BUN), serum creatinine, total bilirubin)
- EBV and CMV PCR in the blood monthly (+/- 2 weeks) to 6 months.
- Reticulocyte count (at 6 months only, Home MDs only if available)
- Thyroid function tests (at 6 months only +/- 1 month)
- Bone marrow biopsy and aspiration with cytogenetics (6 months +/- 1 month only)
- Peripheral blood flow cytometry (6 months +/- 1 month only)
- A repeat research apheresis collection (see section 7.0, Lab research studies)

